7.6 Safety Laboratory Tests

Standard laboratory hematology, serum chemistry, urinalysis, and hepatitis B, hepatitis C and HIV screening will be processed and reported by a central laboratory (Eurofins) at various timepoints, per Schedule of Assessments ([Table 1](#)).

Hematology: complete blood count to include red cell count, hemoglobin level, hematocrit level, white cell count with differential, and platelet count.

Serum chemistry: blood urea nitrogen, creatinine, uric acid, total bilirubin, sodium, potassium, calcium, chloride, bicarbonate, alkaline phosphatase (ALP), AST, ALT, lactate dehydrogenase, gamma-glutamyl transferase, CPK, albumin, total protein, total cholesterol, triglycerides, C-reactive protein, and glucose.

Urinalysis: pH, protein, glucose, ketones, bilirubin, blood, urobilinogen, nitrites, leucocytes, and specific gravity; microscopic analysis if abnormal.

Hepatitis and HIV Screening: Hepatitis screen: HBsAg or HBcAb and hepatitis C virus antibody (HCVAb). A hepatitis C viral load test is to be carried out if HCVAb is positive. The patient should be excluded from the study in case of positive hepatitis C viral load test result. If the hepatitis C viral load test result is negative, the patient can be enrolled in the study. *Note: Patients who test positive for HBcAb, negative for HBsAg and subsequently confirmed positive for HBsAb, indicating resolved natural infection (confirmed by negative HBV-DNA), may participate. Patients with positive HCV may participate if subsequent viral load is confirmed negative.*

Additional Testing: Additional and repeat testing for any safety parameter may be performed at the discretion of the Investigator in the interest of patient safety. If emergency testing is needed or a laboratory test is not available in the central lab, a local lab may be used. All laboratory test results should be recorded in the medical record and captured in the EDC under adverse event if the results are abnormal and clinically significant.

As specified in the laboratory manual, all laboratory safety tests will be performed by a central laboratory (Eurofins). Details of all methodology and reference ranges are provided in the laboratory manual.

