9.6 Safety Data Analysis

Adverse events will be coded using the MedDRA. Treatment-emergent adverse events (TEAEs) are defined as any AEs occurred or worsen during the treatment period from first administration of study treatment to end of the follow-up period, whether or not considered related to the treatment. The incidence of TEAEs will be presented overall, by system organ class (SOC), and by preferred term for each treatment group. Incidence of AEs by severity and relationship to study drug will also be presented for each treatment group. Deaths, SAEs, AESIs and adverse events resulting in discontinuation from the study will be summarized by treatment group.

Safety laboratory parameters, ADA and NAb, vital signs, ECG parameters will be summarized by treatment group and by scheduled visit. Change from Baseline in these continuous parameters will also be summarized by treatment group and by scheduled visit.

For AESI, the percentage of subjects with incident AE, the risk difference, its 95% confidence interval, and p-value will be provided. The confidence intervals and p-values are not adjusted for multiplicity and therefore must be considered accordingly. The requirement will be at least 4 subjects in any treatment arm. The cut-off of at least 4 events was chosen because the 95% confidence interval for the between-group difference in percent incidence will always include zero when treatment groups of equal size each have less than 4 events and so adds little to the interpretation of potentially meaningful differences.

Two approaches will be used for handling safety data occurring after the initiation of rescue therapy. The first approach will exclude all data following the initiation of rescue, in order to avoid the confounding influence of the rescue therapy. The second approach will include data following the initiation of rescue therapy. For the overall study analyses, the “including rescue” approach will be considered primary for all safety endpoints.

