**Table 1. Analysis Window for Safety Parameters**

Nominal Visit	Analysis Visit	Target Study Day	Minimum Study Day	Maximum Study Day
Visit 2	Baseline	1	-30	1
Visit 3	Week 1	8	2	11
Visit 4	Week 2	15	12	18
Visit 5	Week 4	29	26	32
Visit 6	Week 6	43	40	46
Visit 7	Week 8	57	54	60
Visit 8	Week 10	71	68	74
Visit 9	Week 12	85	82	88
Visit 10	Week 14	99	96	102
Visit 11	Week 16	113	110	116
Visit 12	Week 18	127	124	130
Visit 13	Week 20	141	138	144
Visit 14	Week 22	155	152	158
Visit 15	Week 24 (End of Treatment)	169	166	172
Visit 16	Week 28	197	192	202
Visit 17	Week 32 (End of Study)	225	220	230

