**Table 5. Analysis Window for Other Efficacy Parameters**

Nominal Visit	Analysis Visit	Minimum Study Day	Maximum Study Day
Visit 2	Baseline	-7	-1
Visit 3	Week 1	1	8
Visit 4	Week 2	9	15
Visit 5	Week 4	23	29
Visit 6	Week 6	37	43
Visit 7	Week 8	51	57
Visit 8	Week 10	65	71
Visit 9	Week 12	79	85
Visit 10	Week 14	93	99
Visit 11	Week 16	107	113
Visit 12	Week 18	121	127
Visit 13	Week 20	135	141
Visit 14	Week 22	149	155

Visit 15	Week 24 (End of Treatment)	163	169
Visit 16	Week 28	191	197
Visit 17	Week 32 (End of Study)	219	225

If more than one assessment is available within the same analysis visit, the assessment with closest study day to the target study day will be reported for the analysis window. If two observations exist with the same distance to the target study day, then the first observation will be used.

Unscheduled visit will not be used in the analysis if scheduled visit is available. Unscheduled visit will be used in the analysis only if scheduled visit is not available.

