#### 4.12.4 Clinical Laboratory Evaluation

All laboratory values will be reported and summarized using standard international (SI) units ([Appendix D – Laboratory SI U](#)). CTCAE v5.0 will be used for the laboratory toxicity grade ([Appendix E: CTCAE V5.0 Toxicity Grading for Laboratory Parameters](#)).

The following central laboratory tests will be summarized:

- Hematology: red blood cell count, hemoglobin level, hematocrit level, white blood cell count with differential, and platelet count
- Serum Chemistry: blood urea nitrogen (BUN), creatinine, uric acid, total bilirubin, sodium, potassium, calcium, chloride, bicarbonate, alkaline phosphatase (ALP), aspartate aminotransferase (AST), alanine aminotransferase (ALT), lactate dehydrogenase (LDH), gamma-glutamyltransferase (GGT), creatine phosphokinase (CPK), albumin, total protein, total cholesterol, triglycerides, C-reactive protein (CRP), and glucose
- Urinalysis: pH, protein, glucose, ketones, bilirubin, blood (hemoglobin), urobilinogen, nitrites, leukocytes, and specific gravity; microscopic analysis if abnormal

Continuous test results for each parameter and changes from baseline will be summarized at each visit by treatment and overall using descriptive statistics. Categorical test results for each parameter will be summarized at each visit by treatment and overall using frequencies and percentages. Shift of laboratory toxicity grade from baseline to each post-baseline visit will be summarized by treatment and overall. By-subject listings of laboratory parameters will also be provided.

Laboratory values will be listed by subject and study time point including changes from baseline, where available. All values outside the clinical reference ranges will be flagged in the data listings. The abnormal values will be flagged with 'L' for values below the lower limit of the clinical reference range and 'H' for values above the upper limit of the clinical reference range and included in the listings.

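### A subject's worst post-baseline laboratory grade can be absent from all laboratory tables, because unscheduled results are set aside and CTCAE shifts are tabulated only by visit

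*SAP*

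**What the plan says.** Section 4.3.1 of the SAP sets the analysis windows and closes with rules for choosing one result per window. On unscheduled results it states "Unscheduled visit will not be used in the analysis if scheduled visit is available" and then "Unscheduled visit will be used in the analysis only if scheduled visit is not available". Where a window holds several results, "the assessment with closest study day to the target study day will be reported for the analysis window". The section opens its tables with "Table 1. Analysis Window for Safety Parameters".

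Section 4.12.4 of the SAP describes the laboratory outputs. For continuous results: "Continuous test results for each parameter and changes from baseline will be summarized at each visit by treatment and overall using descriptive statistics". For grades: "Shift of laboratory toxicity grade from baseline to each post-baseline visit will be summarized by treatment and overall". No worst or maximum post-baseline grade is planned. Protocol 9.6 takes the same by-visit approach: "Change from Baseline in these continuous parameters will also be summarized by treatment group and by scheduled visit".

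Protocol 7.6 expects extra tests: "Additional and repeat testing for any safety parameter may be performed at the discretion of the Investigator in the interest of patient safety".

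**The concern.** Repeat safety tests are not a random sample of days. They are often ordered because something needs checking, so some of them may carry the highest value a subject ever has. A by-visit table that prefers the scheduled result, or the result nearest the target day, is reasonable for means over time. It is a poor instrument for finding the worst grade. For AEs the SAP does take the worst severity per subject (4.12.2); laboratory grades have no equivalent.

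This carries more weight since SAP 4.15 moved the focus of the analysis to safety after early termination. A reader comparing arms on laboratory toxicity would rely on the 4.12.4 tables, and these can show a lower worst grade than the subject actually had.

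**Working it through.** **Step 1. Do the rules reach laboratory data?** The closing rules of SAP 4.3.1 follow Table 5, an efficacy table, but nothing limits them to efficacy. The closest-to-target rule needs a target day, and only Table 1 (safety) and Table 2 (CT) list one. The rules therefore cover laboratory results, and neither 4.3.1 nor 4.12.4 makes an exception.

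**Step 2. How many study days lie in no safety window?** Inputs are the minimum and maximum days in SAP Table 1. Window length = maximum − minimum + 1. I assume results are assigned to visits by study day.

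- Week 1: 11 − 2 + 1 = 10 days.
- Weeks 2, 4, …, 24: twelve windows of 7 days = 84 days.
- Covered, Days 2–172: 10 + 84 = 94 of 172 − 2 + 1 = 171 days.
- Uncovered: 171 − 94 = 77 days; 77/171 = 45%.
- Cross-check: eleven gaps of 7 days (19–25, 33–39, …, 159–165) = 77.
- Extended to Day 230: Weeks 28 and 32 add 11 days each, so 116 of 229 are covered and 113 are not; 113/229 = 49%.

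**Step 3. What happens to an unscheduled result on a given day?** Scheduled post-baseline chemistry and hematology fall at Weeks 1, 4, 8, 12, 16, 20, 24, 28 and 32. With screening and baseline that makes 11 samples, which matches Protocol Table 3. For Days 2–172:

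| Where the day falls | Days | Fate of an unscheduled result |
|---|---|---|
| Window with a scheduled laboratory test | 10 + 6 × 7 = 52 | Dropped if the scheduled result exists |
| Window without one (Weeks 2, 6, 10, 14, 18, 22) | 6 × 7 = 42 | Can be used |
| No window | 77 | Maps to no analysis visit |
| Total | 171 | |

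Table 1 also has no row for the Early Termination Visit, although Protocol 6.19 collects safety laboratory samples there. Such a sample on an uncovered day has no analysis visit either.

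**Step 4. Illustration.** A subject has a grade 1 CPK at the scheduled Week 8 test on Day 57 and a grade 3 CPK on an unscheduled repeat on Day 59. Both lie in the Day 54–60 window. The scheduled value is used, so the Week 8 shift shows grade 1. If no other tabulated CPK reaches grade 3, the laboratory tables contain no grade 3 for this subject.

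**Step 5. When is it absent from every summary table?** The value must also miss the AE and AESI tables.

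- Under Protocol 7.6 and 8.2, a laboratory abnormality becomes an AE when the investigator judges it clinically significant.
- The only laboratory threshold among the AESIs (SAP 4.12.3) is AST/ALT above 5 × ULN.

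What remains is a value judged not clinically significant: for example a CPK, neutrophil, platelet or bilirubin peak, all graded in SAP Appendix E, or an ALT/AST value at or below 5 × ULN.

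**Step 6. Direction.** The maximum over a subset of a subject's values cannot exceed the maximum over all of them. Dropping results therefore lowers the worst tabulated grade or leaves it unchanged; it cannot raise it.

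**The case against.** The strongest reply is that other routes catch the cases that matter. SAP 4.12.2 tabulates treatment-emergent AEs by maximum severity and those of grade 3 or higher. Protocol 7.6 requires the investigator to review and sign every report and state the clinical significance of each flagged value. All values are listed by subject with out-of-range flags, and in a small, terminated trial listings are a workable place to look. These points stand, and they narrow the gap to the cases in Step 5. They do not close it: the AE route mostly depends on a judgement, and the listings, as described, give neither CTCAE grade nor incidence by arm.

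Three stronger readings are tempting, and the documents do not support them.

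- *A reader might infer that even a grade 3 ALT could vanish from every table.* In SAP Appendix E, grade 3 starts above 5 × ULN if baseline was normal, or above 5 × baseline if abnormal. With a raised baseline the latter also exceeds 5 × ULN. Such a value meets the AESI criterion, and the AESI route does not exclude unscheduled results.
- *A reader might infer that laboratory toxicity is understated throughout.* A repeat may be lower than the scheduled value that prompted it, and that scheduled value is already tabulated. Loss occurs only when the dropped grade exceeds every tabulated grade. The SAP also plans by-visit shifts, not an incidence estimate that could be called biased.
- *A reader might say that a repeat has a better than even chance of falling in no window.* Restricting the count to Days 19–165 gives 77/147 = 52%, but that leaves out the covered days at both ends. No such percentage is a probability for real repeats, which do not fall on random days. In 42 of the 171 days an unscheduled result can be used.

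**Conclusion.** The concern holds in a limited form. By stated rule, a subject's worst post-baseline CTCAE grade can be absent from all laboratory tables, either because a scheduled result displaces it or because its day lies in no safety window (45% of Days 2–172, 49% of Days 2–230). Absence from every summary table needs the further condition that the value was not reported as an AE or AESI. The value is not lost from the report, since the listings keep it.

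The direction of the loss is certain and its size is not: the documents do not give the number of repeat tests or how often a repeat exceeds the scheduled grade. The conclusion assumes that the scheduled-result preference is applied within each window and that visits are assigned by study day. The gap is worth closing because safety is now the focus of the analysis.

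**What to change.** In SAP 4.3.1, state that the unscheduled-visit and closest-to-target rules apply to by-visit summaries only.

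In SAP 4.12.4, add a shift table from baseline grade to worst post-baseline CTCAE grade, per parameter and by arm, using all scheduled, unscheduled and early-termination laboratory results held in the database, whether or not they fall in a window.

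The cost is one extra table. There is one limit to footnote. Protocol 7.6 allows local laboratories for emergency or unavailable tests, SAP 4.12.4 summarises central laboratory tests, and the protocol ties database capture of laboratory results as AEs to clinical significance. Local results may therefore be held only in part, and the table should say which sources it includes.

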#### 4.3.2 Handling of Incomplete Dates

Every effort will be undertaken to avoid any missing or incomplete data, and missing data will not be imputed unless specified. If variables are imputed, the analysis dataset will contain a new variable with imputed value and the original variable will contain the original missing value.

Inevitable partial dates will be imputed for start/end dates of AEs or concomitant medications.

Incomplete dates of medical history will not be imputed.

##### Partial AE Start Date

- If only day is missing, then it will be set to:
  - First day of the month that the AE occurred, if month/year of the AE start date is different than the month/year of the first dose date.
  - The day of first dose date, if month/year of the AE start date is the same as month/year of the first dose date and month/year of the AE end date is different.
  - The day of first dose date or day of AE end date, whichever is earliest, if the month/year of the AE start and month/year of the first dose date and month/year of the AE end date are the same.
- If only month is missing, then it will be set to the earliest of the following:
  - January, as long as this date is after the first dose date
  - Month of the first dose date, if this date is the same day and year that the AE occurred
- If the day and month are both missing, then it will be set to the earliest of the following:
  - January 1 of the year, as long as this date is after the first dose date
  - Month and day of the first dose date, if this date is the same year that the AE occurred
  - The AE end date
- If dates are completely missing, then no imputation will be made.

##### Partial AE End Date

- If only day is missing, then it will be set to the earliest of the last follow-up date, last day of the month, or the date of death.
- If only month is missing, then it will be set to the earliest of the last follow-up date, December, or the date of death.

- If year is missing or AE is ongoing, the end date will not be imputed.
- If dates are completely missing, then no imputation will be made.

If the imputed AE end date is before the corresponding AE start date, then the AE end date will be set to the AE start date.

The same rule above will be applied to the start and end dates of concomitant medications.

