### 4.2 Definitions

#### Age at Baseline

Age will be calculated using the date of birth and date of the baseline visit as below:

Integer part of [(Date of Baseline Visit – Date of Birth) / 365.25]

Baseline

Unless otherwise specified, baseline is defined as the last non-missing value prior to the first dose of study drug. If time is not collected but the assessment is performed on the same day as the first dose of study drug, it would be considered as baseline.

Baseline Week

For weekly average analysis, baseline week is defined as 7 days prior to the baseline visit (Study day ranges from -7 to -1).

Change from Baseline

Change from baseline is defined as post-baseline value minus baseline value.

Study Day 1

Study day 1 is defined as the date of randomization for untreated randomized subjects or the date of first dose for treated subjects.

Study Day

Study Day will be calculated relative to the date of randomization for untreated randomized subjects and relative to the date of first dose for treated subjects.

If event is prior to the first dose, then study day is calculated as:

$$\text{Date of Event} - \text{Date of First Dose}$$

If event is after the first dose, then study day is calculated as:

$$\text{Date of Event} - \text{Date of First Dose} + 1$$

Duration of Treatment

Duration of Treatment (days) will be calculated as:

$$\text{Last Date of Dose} - \text{First Date of Dose} + 1$$

Treatment-Emergent Adverse Events

Treatment-emergent adverse events are defined as any adverse events occurred or worsen during the treatment-period, whether considered related to the treatment.

Where the AE start date is missing, adverse events will be assumed to be treatment-emergent, unless there is clear evidence (through comparison of partial dates) to suggest that the adverse event started prior to the first dose of study treatment.

Prior and Concomitant Medication

Prior and concomitant medication is defined as any medications that started before the first dose of study drug and stops on or after the first dose of study drug.

Prior Medication

Prior medication is defined as any medications that started and stopped before the first dose of study drug.

Concomitant Medication

Concomitant medication is defined as any medications that started on or after the first dose of study drug.

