## 4.9 Prior and Concomitant Medication

Medication start and stop dates will be compared to the date of first dose of study drug to allow medications to be classified as either Prior only, both Prior and Concomitant, or Concomitant only as defined in [4.2](#). Medications starting after the completion/withdrawal date will not be classified or summarized.

Incomplete start and end date of the medications will be imputed as described in [Error! Reference source not found.](#)

Concomitant medications and Prior and Concomitant medications will be coded using the World Health Organization Drug (WHODrug) Global March 2021 B3 and summarized on Safety [Set](#) by treatment and overall. Subjects with more than one medication in a given ATC level and preferred term will be counted only once.

By-subject listings of prior and concomitant medications will also be provided.

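### SAP 4.3.2 applies the AE start-date rule to medications, so a background medicine with a year-only start before the first-dose year is dated to its stop date or left undated

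*SAP*

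**What the plan says.** SAP 4.3.2 gives start-date and end-date imputation rules written for AEs and closes with the sentence "The same rule above will be applied to the start and end dates of concomitant medications". SAP 4.9 also says that incomplete medication dates are imputed, without limiting this to one category. Its cross-reference is broken, but 4.3.2 is the only section that holds such a rule.

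For a year-only start the rule reads "If the day and month are both missing, then it will be set to the earliest of the following", and three candidates are then listed:

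- The first is conditional on falling after dosing began: "January 1 of the year, as long as this date is after the first dose date".
- The second is conditional on a matching calendar year: "Month and day of the first dose date, if this date is the same year that the AE occurred".
- The third carries no condition of its own: "the AE end date".

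On end dates it adds: "If year is missing or AE is ongoing, the end date will not be imputed".

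Classification follows in SAP 4.9: "Medication start and stop dates will be compared to the date of first dose of study drug". The categories are defined in SAP 4.2. Prior means started and stopped before first dose. Prior and Concomitant means started before first dose and stopped on or after it. For the third, "Concomitant medication is defined as any medications that started on or after the first dose of study drug". The last two are summarised on the Safety Set by treatment and overall.

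**The concern.** For AEs, pushing a doubtful start to on or after first dose is a sensible lean, because it errs towards counting an event as treatment-emergent. For medicines the same lean removes the distinction that SAP 4.2 and 4.9 set up between background treatment and treatment begun on study.

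That distinction has meaning in this trial, which tests an add-on to stable background therapy. Protocol 4.4 keeps intranasal steroid on a stable dose and has asthma patients continue any inhaled steroid. Protocol 4.5 allows leukotriene modifiers to continue if taken for at least 30 days before screening, and immunotherapy if on maintenance for at least 90 days. Such medicines may have begun years earlier, and a start recorded only to the year is plausible for them. If the rule mislabels them, the medication summaries show permitted background as new on-study treatment, or cannot place it at all.

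**Working it through.** There is no figure in the plan to reproduce on this point. The check applies the wording of SAP 4.3.2, 4.2 and 4.9 literally.

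**Inputs.** Two first-dose dates are assumed, 15 September 2021 and 10 February 2022; SAP 4.15 puts the start of the trial in June 2021. Recorded start years run from 2015 to the first-dose year. Stop status is ongoing, stopped on study (assumed 20 March 2022), or stopped before dosing (assumed the first day of the first-dose month).

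**Rule.** Imputed start = earliest of the eligible candidates:

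1. 1 January of year Y, eligible only if after first dose. For Y before the first-dose year it never is.
2. The first-dose date, eligible only if Y is the first-dose year. For an earlier Y it never is.
3. The end date, eligible only if there is one. An ongoing record has none, and none is imputed.

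So for an earlier Y only candidate 3 can remain, and for an ongoing medicine nothing remains.

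**Worked example.** Start 2015, first dose 15 September 2021, stopped 20 March 2022. 1 January 2015 is not after first dose, and 2015 is not 2021. The start is therefore set to 20 March 2022, which is after first dose, so the class is Concomitant. The same medicine still ongoing has no start date, and no SAP 4.2 definition can be applied.

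**All cases run.**

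| Recorded start year | Stop status | Cases | Imputed start | Resulting class | Class implied by the recorded dates |
|---|---|---|---|---|---|
| Before first-dose year | Ongoing | 5 | None | Unclassifiable | Prior and Concomitant |
| Before first-dose year | On study | 5 | Stop date | Concomitant | Prior and Concomitant |
| Before first-dose year | Before dosing | 5 | Stop date | Prior | Prior |
| First-dose year | Ongoing or on study | 4 | First-dose date | Concomitant | Not determined |
| First-dose year | Before dosing | 2 | Stop date | Prior | Prior |

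The five earlier-year combinations are 2015 and 2020 for the first date, and 2015, 2020 and 2021 for the second. All 5 + 5 = 10 earlier-year cases still in use at first dose come out wrong or unclassifiable. With 1 January of the recorded year as the imputed start, and ongoing treated as continuing, all ten become Prior and Concomitant, and the five stopped before dosing stay Prior.

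**Is there a safeguard elsewhere?** SAP 4.2 lets a comparison of partial dates rule out treatment emergence for an AE with a missing start date. No such provision is given for medications.

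**The case against.** Several points on the other side are sound.

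- **Pooling.** SAP 4.9 names the two categories in one sentence and does not say that they are tabulated separately; Protocol 9.13 plans one concomitant-medication summary. If they are pooled, a stopped-on-study record changes label but no count. Only the ongoing, undated record could matter, and no text says that such a record is dropped.
- **Visibility.** SAP 4.3.2 keeps the original variable beside any imputed one, and SAP 4.9 provides by-subject listings, so the true partial date can be recovered.
- **Reach.** A start missing only the day, in a month before the first-dose month, goes to the first of that month and is classified correctly. Medicines stopped before dosing are also classified correctly. Patients using another intranasal steroid switch to mometasone at Visit 1, so that mometasone start should be a known visit date.

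These points limit the harm but do not repair the rule. It could be argued that the carry-over sentence concerns only medicines already known to be concomitant. That does not work, because SAP 4.9 uses the dates to decide the category.

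A reader might also infer that starts recorded only as the first-dose year, or only as the first-dose month, are misclassified. The documents do not support that. The order relative to first dose is unknown there, and assigning the first-dose date is a convention. Replacing it with 1 January or the first of the month would hide genuine on-study starts.

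**Conclusion.** The rule is wrong as written for one defined group: medicines with a year-only start in a year before the first-dose year that were still in use at first dose. Those stopped on study are classed Concomitant, and those ongoing cannot be classified, although the recorded year settles that both are Prior and Concomitant. This follows from the text and needs no assumption about the data.

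The consequence is modest. It touches only descriptive medication summaries on the Safety Set, which SAP 4.15 does not withdraw when it refocuses the analysis on safety. No endpoint, hypothesis test or AE result is affected, and the effect on counts is smaller if the categories are pooled.

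Two further inferences should be resisted. A reader might scale an affected-record count from the planned 74 asthma patients. The documents give no share of year-only dates and no number of such medicines per patient, and SAP 4.15 reports early termination with a small sample, so no count can be derived. A reader might also conclude that the AE rule needs the same repair. AEs are recorded only from consent, screening lasts up to 31 days, and SAP 4.2 already compares partial dates for AEs, so that change has little basis.

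**What to change.** In SAP 4.3.2, replace the carry-over sentence, as far as it concerns medication start dates, with a short medication rule:

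- When the recorded start year, or year and month, is before that of first dose, classify the medicine as started before first dose.
- In that situation impute a year-only start to 1 January of the recorded year, and never to the end date.
- Treat a medicine marked ongoing as continuing after first dose, so that it can meet the Prior and Concomitant definition.
- Keep the present convention, imputing to the first-dose date, for starts in the first-dose year or month where the order is unknown.

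Leave the AE rule unchanged. It would also help to state in SAP 4.9 whether the two categories are tabulated separately or pooled, and to repair the cross-reference.

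The cost is a few lines of SAP text and one derivation program. For earlier-year starts there is no trade-off, because the recorded year already fixes the order.
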